COVID-19 Vaccinations With a Sweepstakes

NCT04951310

6/7/2021

COVID-19 Lottery Study Pre-Registration

1) Have any data been collected for this study already? No.

2) What's the main question being asked or hypothesis being tested in this study?

We will measure the effectiveness of a COVID-19 vaccination sweepstakes by analyzing COVID-19 vaccination data from the City of Philadelphia and neighboring regions. The sweepstakes will award multiple prizes every two weeks for at least six weeks. Half of the prizes will be awarded to Philadelphia residents in "selected" zip codes that are randomly selected from a list of 20 under-vaccinated zip codes in the city. selected zip codes will be announced two weeks prior to each drawing. The other half of prizes will be awarded to Philadelphia residents in the remaining zip codes in Philadelphia. We will examine (1) the effect of the lotteries (and accompanying attention that they bring to the vaccination process) on Philadelphia resident vaccination rates relative to people living in neighboring counties and cities and (2) the effect on vaccination rates of selected zip code residents compared to residents from other Philadelphia zip codes that were eligible for this designation ("potentially selected").

3) Describe the key dependent variable(s) specifying how they will be measured.

The primary outcome is the weekly vaccination rate for residents receiving a first dose of a COVID-19 vaccination in each zip/county/city as measured by local health departments and, for residency, as measured by the Census or other official sources.

(Rate = Total residents receiving a first dose that week / Total residents in that zip/county/city code as measured by the Census or other official sources, at the most recent data available for all geographies of interest. This source as of pre-registering is the American Community Survey 2019.)

4) How many and which conditions will participants be assigned to?

We will partner with the City of Philadelphia to launch a COVID-19 vaccination sweepstakes that will be conducted for at least 6 weeks. The city will be included in the "treatment" condition. Within the city, we will include two pools: a "potentially selected" zip code pool (including the 20 zip codes with the lowest per capita vaccination rates as of May 27, 2021) and a pool with the remaining zip codes. At the start of each two-week period, we will randomly draw one "selected" zip code from our list of 20 under-vaccinated zip codes in the city. Half the prizes in each category will go to those in the "selected" zip code.

[figure not shown]
Our differences-in-differences analysis will compare weekly first-dose COVID-19 vaccination rates in each of the three "selected" zip codes (drawn from 20 "priority" zip codes) against the "potentially selected" zip codes that were not selected. We will also compare COVID-19 vaccination rates in all of Philadelphia (Philadelphia county) with vaccination rates in neighboring Pennsylvania counties (Bucks County, Delaware County, and Montgomery County, as per Roberto et al. 2019) and in one comparison city (Baltimore, as a comparable and nearby city and as per Roberto et al. 2019) over the same time period.

5) Specify exactly which analyses you will conduct to examine the main question/hypothesis. We will conduct 3 main analyses:

1. Comparing across cities

To analyze the effect of living in Philadelphia as compared with neighboring counties, we will run a standard difference-in-differences model for weekly COVID-19 vaccination rates by county in the weeks leading up to, during, and after the intervention period. We will include data from May 2, 2021 through August 14, 2021 in this analysis (5 weeks of pre-intervention, 6 weeks of intervention, and 4 weeks of

post-intervention). The analysis will begin by showing a graphical event study representation of the results as follows (graph uses hypothetical data):

Hypothetical Figure 1: (linked http://bit.ly/BCFGPhilVaxPreReg)

The graph above is created by regressing the weekly first-dose COVID-19 vaccination rate for each county on county fixed effects, week fixed effects, and indicators for pre-treatment and post-treatment effects (as described, for example, in Cunningham 2021) with the week just before the treatment period serving as the comparison group. This plot allows us to see the timing/dynamics of the treatment effect and also provides evidence regarding the parallel-trends assumption that is always made in a diff-in-diff analysis by checking for pre-treatment differences in trends.

[figure not shown]
In addition to the graphical analysis above, we will also produce the standard diff-in-diff 2x2 estimate by taking the average vaccination rate pre-treatment for each city and the average vaccination rate during the treatment period for each city and regressing these DVs on City Indicators, a Treatment Indicator, and a Philadelphia*Treatment indicator. The coefficient on the interaction term will be our preferred estimate of the overall effect of the lotteries' impact on Philadelphia relative to nearby cities.

2. Comparing across counties

We will do the exact same analysis as discussed above to test the lottery's impact on Philadelphia relative to nearby Pennsylvania counties (Bucks County, Delaware County, and Montgomery County). We will simply replace the weekly city vaccination rates in the above regressions with the weekly county vaccination rates and include county indicators instead of city indicators.

3. Comparing across zip codes

To analyze the impact of being chosen as a "selected" zip code, we will do a similar analysis to the one above for each of the three "selected" zip codes. Once again, we will begin by showing a graphical event study representation of the results, but this time we will be comparing a "selected" zip code to the other "potentially selected" zip codes that did not win ("unselected zip codes"). The analysis for the first "selected" zip code may look something like the following (graph uses hypothetical data):

The graph above is created by regressing the weekly first-dose COVID-19 vaccination rate for each "potentially selected" zip code (20 total) on zip code fixed effects, week fixed effects, and indicators for pre-treatment and post-treatment effects (as described, for example, in Cunningham 2021). This plot allows us to see the timing/dynamics of the treatment effect and also provides evidence regarding the parallel-trends assumption that is always made in a diff-in-diff analysis by checking for pre-treatment differences in trends.

In addition to the graphical analysis above, we will also produce the standard diff-in-diff 2x2 estimate by taking the average vaccination rate pre-treatment for each zip code and the average vaccination rate during the treatment period for each zip code and regressing these DVs on Zip Code Indicators, a Treatment Indicator, and a selected Zip Code*Treatment indicator. The coefficient on the interaction term will be our preferred estimate of the overall effect of each lottery's impact on each of the "selected" zip codes relative to "unselected" zip codes (across the full treatment period, this will be 17 remaining zip codes).

There will be three different figures above for each of the 2-week lottery periods (one figure for each of the 3 "selected" zip codes). After showing the effects separately for each of the 3 "selected" zip codes, we can also do a pooled analysis where we combine/average the results across the 3 "selected" zip code analyses. To do this, we can stack the data from the 3 studies and produce just one figure like the one above where we show the same results relative to week 0 of the event window. To produce the final overall effect of the lotteries impact on the "selected" zip code, we will regress the weekly vaccination rate for each zip code on zip code fixed effects, week relative to treatment fixed effects (1 week before treatment, 2 weeks before treatment, etc.), and a "selected" zipcode*treatment indicator that equals one when the "selected" zip code was in the treatment period.

6) Describe exactly how outliers will be defined and handled, and your precise rule(s) for excluding observations.

No outliers will be excluded.

7) How many observations will be collected or what will determine sample size?

No need to justify the decision, but be precise about exactly how the number will be determined. Weekly vaccination totals by zip code in Philadelphia will be collected from the Philadelphia department of public health. Weekly vaccination totals by county will be collected from the CDC. For each region of interest we will include weekly vaccination data from May 2nd through August 14th (for 5 weeks prior to the announcement of the sweepstakes, during the entire sweepstakes, and for 4 weeks after the conclusion of the sweepstakes.)

8) Anything else you would like to pre-register?

Assuming we find positive effects from the treatment, the increased vaccinations could be a result of persuading people who would not have otherwise been vaccinated to become vaccinated or a result of causing people who were eventually going to be vaccinated to move up their vaccination date. If the latter is true, we may see a reduction in vaccination rates in the post-treatment period. This is what in economics has been referred to as a "harvesting" effect where you are simply causing intertemporal substitution for when people perform an action like vaccination. The graphs discussed above will allow us to look for this intertemporal substitution effect by seeing if the dots are less than 0% in the post-treatment period and a similar analysis as listed above will allow us to estimate the magnitude of this substitution.

Assuming we are able to collect data on awareness of the lottery through our partner research organizations we also intend to run a mediation analysis with "awareness" as a mediator.

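### The non-randomised city and county comparisons are estimated only in percentage points, so a proportional change common to all areas would appear as a lottery effect if starting rates differ

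*Combined protocol and SAP*

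**What the plan says.** Section 3 defines the outcome as a simple proportion of all residents: "Rate = Total residents receiving a first dose that week / Total residents in that zip/county/city code".

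Section 5, Comparing across cities, says the plan will "run a standard difference-in-differences model for weekly COVID-19 vaccination rates by county" and describes two analyses of that outcome:

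- An event study, obtained by "regressing the weekly first-dose COVID-19 vaccination rate for each county on county fixed effects, week fixed effects, and indicators" for the weeks before and after treatment starts.
- A 2x2 estimate, obtained by "taking the average vaccination rate pre-treatment for each city and the average vaccination rate during the treatment period for each city" and regressing these means on city, treatment and Philadelphia-by-treatment indicators. Of this the plan says: "The coefficient on the interaction term will be our preferred estimate of the overall effect".

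Comparing across counties repeats this: "We will do the exact same analysis as discussed above to test the lottery's impact on Philadelphia", with three Pennsylvania counties in place of Baltimore. Neither analysis names a log-rate, count or ratio model.

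The stated safeguard is the event-study plot, which is to give evidence on parallel trends "by checking for pre-treatment differences in trends". No consequence is given if the trends are not parallel. Section 8 reads harvesting from the sign of the post-treatment points on the same plot.

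**The concern.** A difference-in-differences model on the raw rate assumes that, without the lottery, Philadelphia and its comparators would have changed by the same number of percentage points. If they would instead have changed by the same proportion, an area with a lower starting rate loses fewer points, and the model counts the difference as a lottery effect.

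Random selection protects only the zip-code comparison. Philadelphia is not randomised against Baltimore or the three counties, and the plan has no matching or baseline scaling to bring starting rates together. The size of the city-wide estimate, and possibly its sign, could therefore depend on a choice of scale that the plan makes without comment. The harvesting reading uses the same scale and is exposed in the same way.

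**Working it through.** **Inputs from the documents.** There are 15 weeks: 5 before, 6 during and 4 after the intervention (Section 5). The outcome is the raw weekly rate and the preferred estimate is the additive interaction. The plan states no figure for this comparison that could be reproduced.

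**Assumed inputs.** The true lottery effect is zero. All areas decline by the same proportion d each week. Philadelphia's rate is k times the comparator's.

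**Step 1, algebra.** With pre-period rates P and C and a common proportional fall f in the period mean:

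DiD = [P(1 - f) - P] - [C(1 - f) - C] = -f(P - C).

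With P = kC, the bias as a share of Philadelphia's own pre-period rate is f(1 - k)/k. On the log scale, log(1 - f) - log(1 - f) = 0 for any k.

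**Step 2, the fall f.** This is 1 minus the mean of (1 - d)^t over weeks 6-11 divided by its mean over weeks 1-5. For d = 5%: 1 - 0.6833/0.9049 = 0.2449.

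**Step 3, the bias.** For k = 0.75 and d = 5%: 0.2449 × 0.25/0.75 = +8.2%. The range is:

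| Weekly decline | f | k = 0.50 | k = 0.75 | k = 1.00 | k = 1.25 |
|---|---|---|---|---|---|
| 3% | 0.154 | +15.4% | +5.1% | 0 | -3.1% |
| 5% | 0.245 | +24.5% | +8.2% | 0 | -4.9% |
| 10% | 0.437 | +43.7% | +14.6% | 0 | -8.7% |

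The result is the same with one comparison city or with three counties that share the rate C.

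**Step 4, what the pre-trend plot would show.** Take d = 5% and scale the comparator to a pre-period mean of 1. It falls from 1/0.9049 = 1.105 in week 1 to 0.8145/0.9049 = 0.900 in week 5, a drop of 0.205. The gap between areas therefore moves by 0.205/0.2449 = 84% of the bias within the pre-period. The corresponding figures are 79% for d = 3% and 96% for d = 10%. A smooth decline already under way would thus be visible. A fall that begins when treatment begins would leave the pre-period points flat. For example, with P = 0.8%, C = 1.0% and a step fall of 30%, the bias is -0.3 × (0.8 - 1.0) = +0.06 percentage points with no warning.

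**Step 5, degrees of freedom.** The two-city event study has 2 × 15 = 30 rows and 2 area + 14 week + 14 lead and lag terms = 30 parameters (rank 30), leaving none. The county version has 4 × 15 = 60 rows and 4 + 14 + 14 = 32 parameters (rank 32), leaving 28.

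**Step 6, harvesting.** With d = 5% and no lottery effect, the four post-period points lie between -5% and -7% of Philadelphia's pre-period rate for k = 1.25, which would look like harvesting. For k = 0.75 they lie between +9% and +12%, which could hide it.

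**The case against.** The main objection is that no premise of the calculation comes from the documents. They give no starting rates, do not say that first doses are falling, and do not say that any fall would be proportional. If the common change is additive, the planned model is the unbiased one and the log model is wrong. With P = 0.8%, C = 1.0% and a fall of 0.3 points in both, the rate ratios are 0.5/0.8 = 0.625 and 0.7/1.0 = 0.70, and 0.625/0.70 = 0.89, a false 11% reduction on the log scale. This stands. It is why the log model belongs beside the planned model and should not replace it.

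A reader might also infer that, because a rate cannot go below zero, areas with different starting rates cannot lose equal numbers of points, so the planned model must fail. The figures do not support that. If the lower-rate area is given the same absolute weekly losses as the higher-rate area, it stays above zero through week 11 in 8 of the 9 scenarios with unequal starting rates. The exception is k = 0.50 with a 10% decline. The bias comes from the proportional assumption, not from the floor.

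It may further be said that the plot is an adequate safeguard. In part it is: Step 4 shows it would display drift nearly as large as the bias under a smooth decline. A lack of residual degrees of freedom removes model-based standard errors, not the plotted points, and it affects only the two-city version. The two comparator sets also help, because a scale bias would differ between them if their starting rates differ. What remains is that the plot is a diagnostic on the same additive scale. It yields no corrected estimate, and the plan attaches no action to it.

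**Conclusion.** The concern holds as a conditional one. The plan fixes a single scale for two non-randomised comparisons, and the preferred estimate depends on that scale whenever starting rates differ and uptake moves proportionally. Under a common weekly decline of 3% to 10%, the bias runs from -9% to +44% of Philadelphia's pre-period rate for k between 0.50 and 1.25. It is about +8% at k = 0.75 and d = 5%. These are illustrations under assumed rates, not estimates for this study.

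A reader might conclude that the sign depends only on which area started higher. It does not. It also depends on whether the common movement is a fall or a rise, and there is no bias if that movement is additive. Nor do the documents show that the city-wide result will be wrong. They show that the plan has no analysis that would reveal how far the result depends on scale. The point does not extend to the randomised zip-code comparison. It is a low-cost improvement that limits what may be concluded from the city and county comparisons.

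**What to change.** For Comparing across cities and Comparing across counties in Section 5:

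- Keep the percentage-point model as planned.
- Pre-specify beside it the same model on the log rate, for example a Poisson model of weekly first doses with a log-population offset and area and week effects.
- Show the pre-period coefficients on both scales, and report both estimates with their uncertainty. State how that uncertainty is obtained, because the two-city 2x2 regression has 4 observations and 4 parameters.
- If the two scales differ materially in sign, or in whether an effect is supported, report the city-wide result and any harvesting reading as dependent on scale.
- Do not use agreement in direction alone as the test for claiming an effect. Under a common proportional fall with no lottery effect, the log estimate is centred on zero, so its sign would match the spurious one about half the time.

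The cost is one extra regression per comparison on data already being collected. The downside is a second estimate to report and a more cautious claim if the scales disagree.

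### The preferred 2x2 estimates leave out the post-treatment weeks, so payback cannot change them; no net effect is defined, and the pooled zip model may count payback weeks as untreated time

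*Combined protocol and SAP*

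**What the plan says.** The primary outcome (section 3) is the weekly first-dose rate, a flow and not cumulative coverage. Section 5, analysis 1, sets a window of 5 pre, 6 sweepstakes and 4 post weeks.

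- **City 2x2 (section 5, analysis 1).** The inputs are the pre-treatment average and "the average vaccination rate during the treatment period for each city". "The coefficient on the interaction term will be our preferred estimate of the overall effect". Analysis 2 repeats this for counties.
- **Zip 2x2 (section 5, analysis 3).** The inputs are the pre-treatment average and "the average vaccination rate during the treatment period for each zip code".
- **Pooled zip model (section 5, analysis 3).** "To produce the final overall effect of the lotteries impact on the 'selected' zip code, we will regress" weekly rates on zip effects, relative-week effects and an "indicator that equals one when the 'selected' zip code was in the treatment period".
- **Timing (section 4).** "At the start of each two-week period, we will randomly draw one 'selected' zip code".
- **Data window (section 7).** "For each region of interest we will include weekly vaccination data from May 2nd through August 14th".
- **Harvesting (section 8).** The plan expects lower post-treatment rates if people only moved their date. It will check whether the plotted points fall below zero, and says "a similar analysis as listed above will allow us to estimate the magnitude of this substitution".

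**The concern.** The four post weeks enter none of the 2x2 estimates. A sweepstakes that persuaded new people and one that only brought dates forward give the same preferred coefficient, provided the payback comes after the treatment period. The persuasion-or-timing question is the plan's own (section 8), yet no section writes out the post-treatment contrast or adds it to the gain. A headline labelled as the overall effect could then be read as extra vaccinations when the net over the observed weeks is nil.

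The pooled zip model raises a second issue. Its indicator returns to zero once a selected zip's treatment period ends. Any post weeks left in the regression therefore serve as that zip's own untreated comparison time. Payback lowers that baseline and raises the coefficient, so more harvesting would give a larger final estimate.

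**Working it through.** **1. The plan's window.** 2 May to 14 August 2021 inclusive is 105 days, and 105/7 = 15 weeks = 5 + 6 + 4, as stated. Weeks 1-5 are pre, 6-11 sweepstakes, 12-15 post. The 17 unselected zips also reproduce (20 - 3).

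**2. City/county 2x2.** The documents give no effect size, so assume a lift e = 0.30 percentage points per week for 6 weeks, with a share s repaid evenly over the 4 post weeks.

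- During-minus-pre contrast (the planned 2x2) = e.
- Post-minus-pre contrast = -s x 6e/4 = -0.45s.
- Net through 14 August = 6 x during + 4 x post = 6e(1 - s).

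| Payback s | 2x2 (pp/week) | Post contrast (pp/week) | Net (pp) |
|---|---|---|---|
| 0% | 0.30 | 0 | 1.80 |
| 50% | 0.30 | -0.225 | 0.90 |
| 100% | 0.30 | -0.45 | 0.00 |

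The size of e is assumed. That the 2x2 does not move follows from its definition.

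**3. Zip 2x2.** With a two-week treatment period the same invariance holds. If the period were the full six weeks, some payback would fall inside it. For the first selected zip, assume a lift of 0.10 for two weeks, repaid over the 8 remaining weeks. The weekly payback is s x 0.20/8, so the six-week average is (0.20 - 4 x 0.025s)/6. That is 0.033 at s = 0 and 0.017 at s = 1.

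**4. Pooled zip model.** Let d be the true weekly effect over two weeks, with 2sd repaid evenly over the post weeks in the window. The selected zip's untreated weeks then average -2sd divided by the number of untreated weeks. I checked the results by fitting the stacked regression to noise-free data (3 stacks, each with 1 selected and 17 unselected zips).

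| Weeks in the stack | Formula | s = 0 | s = 0.5 | s = 1 |
|---|---|---|---|---|
| 5 pre, 2 treatment, 4 post | d + 2sd/9 | 1.00d | 1.11d | 1.22d |
| All 15 weeks | d + 2sd/13 | 1.00d | 1.08d | 1.15d |
| Post weeks excluded | d | 1.00d | 1.00d | 1.00d |

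With a selected-by-post term added, full payback gives 1.000d in the 5/2/4 window. Over all 15 weeks, where the zips have unequal numbers of pre and post weeks, it gives 0.991d.

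**5. Precision of a net effect.** Let v be the variance of one weekly treated-minus-comparison difference, with weeks independent.

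- City/county net: 6 + 4 + 10²/5 = 30v. Gain alone: 6 + 6²/5 = 13.2v. SE ratio √(30/13.2) = 1.51, or 1.60 at weekly autocorrelation 0.6.
- Zips with 4 post weeks and p pre weeks: net 6 + 36/p, gain 2 + 4/p. For p = 5, 7, 9 the ratios are 2.17, 2.08, 2.02, or 2.81, 2.71, 2.64 at autocorrelation 0.6.

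**6. Plotted points against a post coefficient (city/county).** The points are measured from the single week before treatment. Their four-week mean has variance 1/4 + 1 = 1.25v, against 1/4 + 1/5 = 0.45v for a contrast with the five-week pre average. The SE ratio is 1.67, or 1.19 at autocorrelation 0.6.

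**7. Overlap for zips.** The selected zips' treatment weeks are 6-7, 8-9 and 10-11, so their first four post weeks are 8-11, 10-13 and 12-15. Of these, 4, 2 and 0 fall while the sweepstakes is running: 6 of 12.

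**8. Horizon.** If the full city/county gain of 6e is repaid over 8 weeks, the net seen at four weeks is 6e - 4 x 6e/8 = 3e. Over 12 weeks it is 6e - 4 x 6e/12 = 4e.

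**The case against.** The strongest reply is that harvesting is already handled. Section 8 names it, plans to inspect the post-treatment points and plans to estimate its size. The natural reading is the same 2x2 with post weeks in place of treatment weeks, and with 5/6/4 weeks stated, the net is then simple arithmetic. A reader might infer that the plan ignores harvesting; section 8 shows that it does not. What stands is narrower: the contrast is given only by cross-reference, and the plan commits to no net summary.

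A second reply is that overall may simply mean averaged over the treatment weeks, since the outcome is a weekly rate and the 2x2 follows a week-by-week plot. Persuasion versus timing is a section 8 question, conditional on a positive effect, and not the main question of section 2. This is fair. The 2x2 is a legitimate estimate, and the label only needs to say which period it covers.

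Third, a reader might infer that the pooled zip estimate is certainly inflated. The documents do not support that. Section 7 carries data to 14 August for every region and no rule drops post weeks, which suggests they are in. But the stacked window is not stated in the available text, and the zip figure is not shown. The inflation is conditional and moderate, and a stacked plot that includes post weeks would also show the dip.

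Fourth, the zip 2x2 invariance needs the two-week reading. The reference in analysis 3 to two-week lottery periods supports it, but the same section also speaks of a full treatment period with 17 remaining zips. The condition must be stated.

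**Conclusion.** The point holds in this form. The city/county 2x2 is a valid treatment-period effect that payback after the treatment period cannot change. Payback within the six sweepstakes weeks does enter it. The zip 2x2 behaves the same way if each treatment period is two weeks. The plan defines no net effect, although it asks the question that a net effect would answer.

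In the pooled zip model, if post weeks are in the stack, the estimate rises by 8 to 11% at half payback and 15 to 22% at full payback; if they are out, it does not rise. These figures assume parallel trends, a constant lift and even payback.

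Two stronger conclusions do not follow: that the 2x2 is biased for what it measures, or that harvesting occurred. This should be corrected before analysis, but it does not undermine the design.

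**What to change.** 1. **Pooled zip model.** State one common event window. Five pre, two treatment and four post weeks is the longest that all three zips share. Add a selected-by-post term, or exclude post weeks.
2. **City and county.** Add a post-versus-pre term measured against the five-week pre average. Beside the 2x2 report net = 6 x during + 4 x post, labelled as the net within the observed window. Use the actual week counts if the sweepstakes runs longer than six weeks.
3. **Label.** Call the 2x2 a treatment-period effect, and state for zips that the period is the two-week lottery, if that is what is meant.
4. **Harvesting.** Base the conclusion on the post coefficient and keep the plotted points as description.

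The work is SAP wording, one extra regressor and one linear combination, on data already scheduled. There are three statistical costs:

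- The city/county net has an SE about 1.5 to 1.6 times that of the cumulative treatment-period effect.
- The net needs parallel trends through the four post weeks. A late differential trend of -x points per week in those weeks would lower it by 4x and look like payback.
- Payback after 14 August stays unseen.

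Zip-level nets, if reported, should be descriptive only. Their SE ratio is 2.0 to 2.8, and half of the stacked post weeks fall while the sweepstakes still runs, so the comparison zips are still exposed to it.

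### The zip event study is written on all 20 pool zip codes, so other lotteries' winners serve as controls, against the plan's own comparator of zips not selected; the pooled estimate inherits this

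*Combined protocol and SAP*

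**What the plan says.** Section 4 sets the comparison as selected zips "against the 'potentially selected' zip codes that were not selected". Section 5, analysis 3 (Comparing across zip codes), repeats this for the event study: one selected zip against the other eligible "zip codes that did not win ('unselected zip codes".

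The regression behind that figure is then written for each eligible "zip code (20 total) on zip code fixed effects, week fixed effects, and indicators for pre-treatment and post-treatment effects". The 2x2 paragraph that follows compares with unselected "zip codes (across the full treatment period, this will be 17 remaining zip codes". For pooling, "we can stack the data from the 3 studies". The pooled regression uses zip code fixed effects, relative-week fixed effects and a selected-zip-by-treatment indicator. It does not list the zips in each stack or say whether zip effects are shared across stacks.

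No sentence says whether a zip that wins one lottery is removed from the controls of the other two.

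**The concern.** With one selected zip per figure, a 20-zip regression has 19 controls. Two of them win another lottery, and the data run across all three lotteries. Those two zips are untreated controls in name only.

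What is mainly at stake is the pooled coefficient, which the plan presents as its final overall effect for selected zips. With all 20 zips in each stack, a winner's treated weeks reappear in the other stacks coded as untreated. If each zip has one fixed effect across stacks, those weeks raise the winner's own baseline and pull the estimate down. If each stack has its own zip effects, treated weeks among the controls fall mostly in the pre-period and push the estimate slightly up. The direction of the bias therefore depends on a choice the plan does not state.

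A lesser matter is that small false dots appear in the figures where the plan looks for non-parallel trends and, under section 8, for harvesting.

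**Working it through.** **Inputs.** Pool of 20 zips and one zip drawn per two-week lottery (section 4). Three selected zips (sections 4 and 5). 2 May to 14 August is 105 days, or 15 weeks = 5 + 6 + 4 (sections 5 and 7).

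**The plan's own figure.** 20 − 3 = 17, reproduced for three distinct winners. The matching regression has 1 + 17 = 18 zips, not 20.

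**Zips per regression under each reading (lotteries 1, 2, 3).**
- Did not win this draw: 20, 20, 20. Controls are 19 each time, never 17.
- Not yet selected: 20, 19, 18.
- Never selected: 18, 18, 18.

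No reading gives both 20 zips in every figure and 17 controls.

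**Assumptions for size.** Noise-free data; effect d in weeks 6–7, 8–9 and 10–11 for winners 1, 2 and 3, and none in other weeks; indicator equal to 1 only for the stack's own winner in its lottery weeks.

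**Pooled coefficient, in units of d, by event window.**

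| Zips in each stack | Zip effects | All weeks | −5 to +1 | −5 to +5 |
|---|---|---|---|---|
| 20 | shared across stacks | 0.917 | 0.907 | 0.885 |
| 20 | stack-by-zip | 1.016 | 1.021 | 1.023 |
| 18 (never-selected controls) | either | 1.000 | 1.000 | 1.000 |

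These values do not change when a common linear or decaying calendar trend is added.

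**Hand check, window −5 to +1** (20 zips × 7 weeks × 3 stacks = 420 rows).
- Shared effects. Take the indicator net of zip and relative-week means. A winner's zip mean is 2/21, the lottery-week mean is 3/60 = 1/20, and the grand mean is 6/420 = 1/70. The six own-lottery cells have residual 1 − 2/21 − 1/20 + 1/70 = 0.8690. Six further cells hold a winner's treated weeks inside another stack, coded 0: winner 1 in stacks 2 and 3, winner 2 in stack 3, two weeks each. Their residual is −2/21 + 1/70 = −0.0810. The coefficient is d(1 − 0.0810/0.8690) = 0.907d.
- Stack-by-zip effects. Stack 1 gives 1. Stack 2 gives 1 + (2/5)/19 = 1.021. Stack 3 gives 1 + 2(2/5)/19 = 1.042. The mean is 1.021d.

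**Figures, 19 controls.** Assume that the reference stated for the county figure, "with the week just before the treatment period serving as the comparison group", also applies to zips, and that other winners get no indicators of their own. One treated control out of 19 shifts a dot by d/19 = 0.053d.
- Lottery 1: treatment dots 1.000d; false dots −0.053d at weeks +2 to +5.
- Lottery 2: treatment dots 1.053d; false dots +0.053d at weeks −7 to −3 and +4 to +7.
- Lottery 3: treatment dots 1.053d; false dots +0.053d at weeks −9 to −5 and +2 to +5.

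Beside a treatment dot at z = 4, a false dot is about 4 × 0.053 = 0.2.

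**Single-lottery 2x2, 19 controls.** If the pre-period is the five pre-sweepstakes weeks, the estimate is 1.000d in each lottery. If it is all weeks before that lottery, lottery 1 gives 1.000d, lottery 2 gives 1 + (2/7)/19 = 1.015d, and lottery 3 gives 1 + 2(2/9)/19 = 1.023d. Never-selected controls give 1.000d throughout.

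**The case against.** The two counts can be read as compatible. The graph is introduced as the one for the first selected zip, and in the first draw one winner plus 19 non-winners makes 20. The 17 is qualified as applying over the full treatment period, that is, after three draws. The 20 may also just restate the pool size. This works for the first figure, but not for all three figures together with 17 controls, and it still leaves other lotteries' winners undealt with.

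A second argument is that the plan speaks of combining or averaging the three analyses, which fits stack-by-zip effects, and then the bias is only 1.6% to 2.3%. That is a fair reading, but the model as written has plain zip code fixed effects, and those give the 8% to 12% understatement.

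The third argument stands: the single-lottery 2x2, the plan's preferred estimate for each lottery, and the figures are barely touched.

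Two stronger inferences are not supported.
- A reader might infer a far larger pooled bias by coding every winner's treated weeks as 1 in all stacks and assuming a steep calendar trend. The indicator is worded for the selected zip in the singular, each stacked analysis has one such zip, and the documents give no such trend.
- A reader might infer that 17 is itself wrong, because the plan "will randomly draw one 'selected' zip code from our list of 20 under-vaccinated zip codes in the city" without mentioning replacement and describes a "COVID-19 vaccination sweepstakes that will be conducted for at least 6 weeks". But the plan repeatedly names three selected zips, counts 17 remaining, and fixes six intervention weeks. Three distinct winners is its working premise, and what is missing there is detail.

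**Conclusion.** The inconsistency is real and should be resolved before analysis. The 20-zip regression does not match the comparator that sections 4 and 5 define, and the pooled model inherits the mismatch. Read literally, the pooled effect is understated by about 8% to 12% (0.885d to 0.917d). With stack-by-zip effects it is overstated by about 2% (1.016d to 1.023d). Restricting controls to never-selected zips gives 1.000d under either choice.

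These sizes rest on three distinct winners, equal effects confined to each winner's two weeks, and the own-zip indicator. They describe bias in the pooled coefficient. They do not show that the single-lottery 2x2 or the figures would mislead in any material way: those move by at most 2.3% of d and d/19 respectively.

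**What to change.** In every zip figure, 2x2 and stack, use that lottery's selected zip plus only the zips never selected in any drawing, and drop the other winners. Replace the 20-zip count with this rule (18 zips with three distinct winners), and say that the 17 follows from it. For the pooled model, state stack-by-zip fixed effects and an indicator equal to 1 only for the stack's own selected zip in its lottery weeks.

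The cost is a row filter and a few sentences; the three-stack data fall from 3 × 20 × 15 = 900 rows to 3 × 18 × 15 = 810. With equal, independent zip variances, using 17 rather than 19 controls raises single-lottery variance by (1 + 1/17)/(1 + 1/19) = 1.0059, about 0.6%.

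The change does not remove bias from effects that last beyond the lottery weeks. With never-selected controls and all 15 weeks, a lasting effect of +0.25d after the lottery gives 0.885d, and −0.25d gives 1.115d. Section 8 anticipates post-period effects of this kind, so that limit should be stated beside the pooled result.
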